9.7.6 Data integration

Results will be presented separately for each data source and aggregate data will be pooled across data sources, if deemed justifiable given differences in data flow/population.

Meta-analysis may be conducted if/as appropriate using standard methods: heterogeneity will be assessed and visualizations such as forest plots be provided. Because of the expected variation in effect estimates of data-sources we recommend random effect models.¹⁹

9.7.7 Missing data

In routinely collected data, absence of a record is usually interpreted as absence of a condition. Missing data per se are rare, but may occur, e.g., in such variables as gestational age, smoking, BMI. The extent of missing data for each study variable will be reported. No imputation is planned.

9.8 Quality control

The source electronic routinely collected data proposed for use in this study undergo standard curation and quality-check procedures by the data custodians. Standard operating procedures or internal process guidance at each research center will be adhered to for the conduct of the study. These procedures will include internal quality audits, rules for secure and confidential data storage, methods to maintain and archive project documents, quality-control procedures for programming, and standards for writing analysis plans. Routine procedures will include checking electronic files, maintaining security and data confidentiality, following analysis plans, and performing quality-control checks of all programs. Each partner should maintain any patient-identifying information securely on site according to internal standard operating procedures or guidance documents. Quality control for the central meta-analysis of the data will be described within project-specific documents.

This study will be conducted in accordance with the GVP, including the European Network of Centres for Pharmacoepidemiology and Pharmacovigilance (ENCePP) Code of Conduct.²⁰

9.9 Limitations of the research methods

An important limitation of the research method is that currently Spikevax is not indicated for use in pregnancy according to the current label, implying that at least at the initial study stages, the number of exposed pregnancies may be low, potentially affecting precision of the resulting estimates of association. Furthermore, owing to typical data flow in routinely collected data, only completed pregnancies (ending in a birth or an abortive outcome) are identifiable. Ongoing pregnancies cannot be identified. A further limitation is heterogeneity of the different data sources in their ability to identify all pregnancy outcomes of interest. Finally, unmeasured confounding due to non-comparability of vaccinated and non-vaccinated pregnancies (healthy or sick vaccinee), at least at the start of the vaccination of pregnant women, cannot be ruled out. If pregnant women with chronic diseases or those taking medication are more likely to be vaccinated, uncontrolled confounding by morbidity will produce an upward bias in the association between vaccination and some AESI, whenever these chronic diseases are themselves associated with adverse outcomes.

A potential misclassification of exposure timing (eg. if LMP is imprecise) may produce a downward bias, if an association exists.

Because, by definition, pregnancy and neonatal outcomes are prevalent outcomes, one cannot enumerate the cohort of conceptuses initiating the follow-up. Early pregnancies that end in a spontaneous abortion and do not lead to a health care record are not detectable in the available data sources. At the same time, shorter pregnancies may be overestimated in the study population because of being identified by pregnancy end.²¹

Finally, for the outcome major congenital malformations, the standard (EUROCAT)¹⁴ definitions recommend follow-up until age 1 year, which will not be available for all neonates in currently defined study populations. This under ascertainment will lower the sensitivity of the outcome, which, if not related to vaccination status, should not bias associations

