This study is planned as analysis of routinely collected health data in secondary automated electronic data sources in Denmark, Italy, Norway, Spain, and the UK, selected based on availability of the required routinely collected data, including information on vaccine brand and frequency of data updates.

Study size

It is estimated that the number of live births available for analysis will range between 20,000 to 100,000 depending on a data source.

Data analysis

Counts and percentages will be presented for categorical variables (woman's age at conception in categories). Means, standard deviations, medians and interquartile ranges will be presented for continuous variables (woman's age at conception). The proportion of missing data will be described when appropriate. For pregnancy complications and adverse pregnancy outcomes, pregnancy will be the unit of observation; for neonatal outcomes, a newborn will be the unit of observation. For the outcomes of congenital malformations and stillbirth, the number at risk will be the total number of live or stillborn children.

Prevalence of each outcome will be computed as number of observations with a given outcome divided by the total number of observations at risk. Prevalence of each outcome will be compared for exposed vs. unexposed pregnancies according to predefined exposure categories and using, whenever necessary, plausible exposure risk windows. For example, for assessing the outcome of congenital malformations, maternal gestational diabetes and hypertensive disorders, births or pregnancies will be classified based on their exposure in the first (or second, if relevant) trimester. For all other neonatal outcomes, exposure any time in pregnancy and per trimester may be considered.

For neonatal deaths, 28-day mortality risks will be computed and compared among live-born neonates. For pregnancy-related death, maternal mortality will be evaluated at any time while pregnant or up to 1 year after pregnancy end.

All relevant analyses will be stratified by country, maternal age, sex, calendar time, trimester and seasonality if applicable.

Milestones

Data collection will continue through 31 March 2023 with a final study report planned by December 2023.

5. Amendments and updates

Write "None" or indicate any substantial amendment and update to the study protocol after the start of data collection in a table as indicated below.

Confidential

Post-marketing safety study for COVID-19 mRNA-1273 vaccine

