Protocol mRNA-1273-P905, Date: 27 September 2021, Version 1.2

Number	Date	Section of study protocol	Amendment or update	Reason
1	Date	Text	Text	Text
2	Date	Text	Text	Text
...	Date	Text	Text	Text

6. Milestones

Milestone	Planned date*
Start of data collection	31 December 2021
End of data collection/data cut for Final report of study results	31 March 2023
Study progress report 1	31 March 2022
Study progress report 2	31 December 2022
Study progress report 3	30 June 2023
Registration in the EU PAS register	Upon approval
Final report of study results	31 December 2023

* Subject to data queues by data custodians; progress report will contain information on study progress and data updates whenever available.

7. Rationale and background

The novel coronavirus SARS-CoV-2 (severe acute respiratory syndrome coronavirus 2) causes coronavirus disease 2019 (COVID-19) and has led to a global pandemic. A mass vaccination campaign is currently underway in Europe.

The mRNA-1273 vaccine candidate was co-developed by the Cambridge, Massachusetts-based biotechnology company Moderna, Inc., and the United States (US) National Institute of Allergy and Infectious Diseases (NIAID), part of the National Institutes of Health. The vaccine, currently known as Spikevax,¹ combines Moderna's mRNA (messenger ribonucleic acid) delivery platform with the stabilized SARS-CoV-2 spike immunogen, developed by NIAID.

The completed COVE Phase 3 efficacy multicentre trial in United States (US) showed 94.1% efficacy of the Spikevax at preventing COVID-19 illness, including severe disease. Aside from transient local and systemic reactions, no safety concerns were identified. Pregnant women were not eligible to participate in that trial.² Preliminary findings from an observational study in the US were not indicative of obvious safety signals among pregnant persons who received mRNA COVID-19 vaccines, but the study indicated the need for longitudinal follow-up in a large number of women.³

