9.2. Setting

This study will be multi-database, utilizing routinely collected health data of various types in five European countries: Denmark, Italy, Norway, Spain, and the United Kingdom. Pregnancies ending between 06 January 2021 (date of the earliest approval of the COVID-19 Moderna Vaccine in Europe) and up to 31 December 2022 will be identified and classified according to the exposure to Spikevax overall, and according to the trimester of exposure. The study period may be extended if the size of the study population is insufficient to study specific outcomes of interest. The source population comprises persons contributing to each participating database. The study databases are representatives of their source population (see Appendix 1 for details). Briefly, in Denmark and Norway, the registries have full population coverage with respect to the available routinely collected data. The regional databases in Italy (ARS) and Spain (SIDIAP) are representative of the underlying regional populations (Tuscany and Catalonia, respectively). The CPRD is broadly representative of the UK population.

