Owing to several limitations specific to routinely collected data on pregnancy, only one data extraction is feasible under this protocol. These limitations include: expected low initial number of Spikevax exposed pregnancies; the need to wait for pregnancy end to be identified; different timing of mother-child linkage in different databases; and less frequent (than other databases) data refreshes on birth registries with the largest number of observations and full population coverage (Denmark and Norway). Figure 2 illustrates the data pathway from pregnancy recording to availability for the analysis.

Figure 2. Data pathway from pregnancy recording to availability for the analysis.

To monitor the number of exposed pregnancies, and thus the feasibility of the pregnancy analysis, the number of Spikevax-exposed pregnancies will be approximated from the available pregnancy indicators, such as records of prenatal visits, or diagnostic codes associated with pregnancies. Such records, as a rule, will not be complete with respect to pregnancy outcomes, but are expected to conservatively estimate the number of pregnancies exposed to Spikevax that will be available for the final analysis. Table 6 summarizes the planned contents of the interim and final study reports.

Table 6 Planned data extractions and contents of study reports.

Milestone	Date	Pregnancy data available from each database				
		Denmark	Italy	Norway	Spain	UK
START OF DATA COLLECTION (AT LEAST ONE DAP EXTRACTS DATA in study mRNA-1273-P904)	31-Dec-21					
Study progress report 1 Planned content: status update providing an overview of progress towards finalization of the study design, counts of pregnancies observed in study mRNA-1273-P904 (preliminary pregnancy counts from 31 December 2021 extraction)	31-Mar-22					
Study progress report 2 Planned content: status update providing an overview of project status, counts of pregnancies observed in study mRNA-1273-P904 (preliminary pregnancy counts from 31 December 2021 extraction)	31-Dec-22					

Study progress report 3 Planned content: status update providing an overview of project status, application for data, initial steps towards execution of planned analyses, counts of pregnancies observed in study mRNA-1273-P904 (preliminary pregnancy counts from 31 December 2021 extraction)	30-Jun-23					
END OF DATA COLLECTION (ALL DAPS EXTRACT DATA FOR PREGNANCY ANALYSES)	31-Mar-23					

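### Follow-up for malformations depends on birth date, and birth date is tied to first-trimester vaccination, so section 9.9 cannot rely on under-ascertainment being unrelated to exposure

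*Protocol*

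**What the plan says.** Protocol section 9.9 notes that the standard malformation definitions "recommend follow-up until age 1 year, which will not be available for all neonates in currently defined study populations". It concludes: "This under ascertainment will lower the sensitivity of the outcome, which, if not related to vaccination status, should not bias associations".

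The dates that decide how long each infant is observed are elsewhere:

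- Section 9.2 includes "Pregnancies ending between 06 January 2021 (date of the earliest approval of the COVID-19 Moderna Vaccine in Europe) and up to 31 December 2022".
- The abstract states "Data collection will continue through 31 March 2023", and section 6 gives the same date for the data cut.
- Section 12 says that "only one data extraction is feasible under this protocol". Its Table 6 expects the latest pregnancy end to be 30 October 2022 in Denmark and Italy, and 31 December 2022 in Norway, Spain and the UK.
- Section 9.3.1 ends the first trimester at LMP+97 days. Section 9.7.2 and Table 4 make the first trimester the exposure window for major malformations.

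Table 4 sets no age at which ascertainment stops, and section 9.7.5 lists no sensitivity analysis for unequal follow-up. On calendar time, section 9.3.3 names calendar year of delivery as a covariate. Section 9.7.4 provides for stratification by calendar time where applicable, without a stratum width.

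**The concern.** Malformations recognised after birth are counted only if they are recorded before the cut. An infant born in January 2021 is observed for over two years, and one born on the last day of 2022 for about three months. If exposed and unexposed infants are born at different times, the share of true malformations that is recorded differs between them even when the vaccine has no effect.

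The protocol treats this loss of sensitivity as harmless on a condition that it does not examine. Major malformations are one of the four primary objectives, and Table 3 expects enough precision to rule out a prevalence ratio of 1.11 in its most favourable row. A bias of several per cent in either direction could hide a modest increase or suggest one that does not exist.

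**Working it through.** **1. The plan's own figure.** Table 3, any major malformation: n₁ = 16,667 exposed, ratio 5:1 (83,335 unexposed), prevalence p = 0.05 in both groups, true ratio 1.

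SE = √[0.95/(0.05 × 16,667) + 0.95/(0.05 × 83,335)] = 0.0370.

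Upper limit at 80% probability: exp[(1.96 + 0.84) × 0.0370] = 1.11. At 90%: exp[(1.96 + 1.28) × 0.0370] = 1.13. Both match. They are precision figures that assume no bias, and serve here only as a yardstick.

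**2. Dates.**

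- Earliest LMP compatible with first-trimester exposure: 6 Jan 2021 − 97 days = 1 Oct 2020. Adding 280 days, the first exposed 40-week birth is on 8 Jul 2021.
- Births from 6 Jan to 7 Jul 2021 at 40 weeks can only be unexposed: 183/725 days = 25% of the window. All have more than a year before the cut.
- Births after 31 Mar 2022 have less than a year: 275/725 = 38%. The minimum is 90 days (31 Dec 2022 to 31 Mar 2023).
- All 2021 births have at least a year. Births in 2022 have 454 down to 90 days, about 15 to 3 months.

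**3. Model for live births.** The protocol gives neither the age at which malformations are recorded nor first-trimester uptake, so both are assumptions. Births are even over 6 Jan 2021 to 31 Dec 2022, at LMP+280 days. The fraction of true malformations recorded by age a days is F(a) = b + (1 − b) × min(a, 365)/365, with b = 0.5 to 0.8 recorded at birth. The true prevalence ratio is 1, so the crude ratio is mean F in exposed divided by mean F in unexposed. Adjusted ratios are Mantel–Haenszel over birth-date strata.

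Hand check, all exposed births in 2022: 90 of 365 days have a full year, and 275 days have a mean age of (364 + 90)/2 = 227. Mean capped fraction = (90 × 365 + 275 × 227)/365² = 0.715. Over the whole window it is (450 × 365 + 275 × 227)/(725 × 365) = 0.857. With b = 0.5 the ratio is (0.5 + 0.5 × 0.715)/(0.5 + 0.5 × 0.857) = 0.858/0.928 = 0.92. Removing the exposed births from the denominator changes only the third decimal.

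**4. Apparent ratio when the truth is 1** (b = 0.5, then b = 0.8). Where a vaccination period is given, the chance of first-trimester exposure is 1 − exp(−0.0015 × first-trimester days inside it). The daily rate is arbitrary.

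| Assumed first-trimester uptake | Crude | Adjusted for year | Adjusted for quarter |
|---|---|---|---|
| Constant from 6 Jan 2021 | 0.960, 0.985 | 1.000, 1.000 | 1.000, 1.000 |
| Exposed births even over 2022 | 0.920, 0.969 | 1.000, 1.000 | 1.000, 1.000 |
| Exposed share rising linearly from 8 Jul 2021 | 0.899, 0.961 | 0.958, 0.985 | 0.998, 0.999 |
| Constant from 21 Jul 2021 | 0.884, 0.956 | 0.959, 0.985 | 0.999, 1.000 |
| Nov 2021–Feb 2022 only | 0.866, 0.949 | 0.938, 0.977 | 1.000, 1.000 |
| Mid-2021 wave: exposed births even over Oct 2021–Jun 2022 | 1.057, 1.022 | 1.085, 1.032 | 1.000, 1.000 |
| Mid-2021 wave: vaccination May–Sep 2021 | 1.063, 1.024 | 1.130, 1.048 | 1.006, 1.003 |

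The share of births with under a year of observation, exposed against unexposed, is 91% against 35% with uptake from 21 Jul 2021, but 33% against 38% with the May–September wave. That is why the sign changes. In the wave, the infants with least follow-up are unexposed births in late 2022. Year adjustment then enlarges the bias, because it concentrates the comparison within 2022.

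**5. Denmark and Italy.** If infant diagnoses there also stop at 30 Oct 2022 (an assumption; Table 6 gives only pregnancy ends), the crude ratio at b = 0.5 falls to 0.76 with uptake from 21 Jul 2021 and to 0.69 with the November–February wave.

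**The case against.** - **The sentence is conditional.** Section 9.9 claims no bias only if under-ascertainment is unrelated to vaccination. That stands: the statement is untested rather than false. But the protocol's own dates make the condition fail in the crude comparison, so it gives no reassurance.
- **Calendar time is already in the plan.** This carries weight. Year of delivery is a key covariate, available in all five databases. It removes the bias entirely in two of the scenarios above and more than halves it in the other late-uptake ones. It does not suffice in general, because follow-up varies from 3 to 15 months within 2022. The calendar-time stratification could suffice, but its width is not fixed and it is listed under subgroup analyses.
- **The SAP may settle it.** Section 9.3.2.1 leaves outcome-specific considerations and population restrictions to the SAP, which was not seen. An ascertainment window may be set there. The year-wide covariate and the section 9.9 reassurance are nevertheless stated in the protocol.
- **A reader might infer that the ratio is biased downward.** The documents do not support a fixed direction. Late or rising uptake gives a downward bias, and sections 9.9 and 12 do expect few exposed pregnancies at first. But no first-trimester uptake curve is given, and the Danish recommendation of July 2021 cited in section 7 concerns the second and third trimesters. A mid-2021 wave reverses the sign.
- **A reader might take the crude figures as the error in the main result.** They are not, since adjusted ratios are planned.
- **The negative control might reveal the problem.** It cannot calibrate it. Infants exposed in the second or third trimester can be born from January 2021, so their follow-up is distributed differently.

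**Conclusion.** The point holds in a limited form. Ascertainment time for malformations is related to first-trimester vaccination through birth date, and the no-bias statement in section 9.9 cannot be relied on.

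With 50–80% of malformations recorded at birth, the crude null ratio is about 0.88–0.97 under late or rising uptake and about 1.02–1.06 under a mid-2021 wave. After adjustment for year of delivery about 0.96–1.09 remains, and 0.94–1.13 if uptake is concentrated in a single short period. For scale, a true ratio of 1.11 could appear as 1.11 × 0.96 = 1.07, or a true 1.00 as 1.09.

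These sizes rest on an assumed recording curve and assumed uptake. If nearly all malformations are recorded at birth, the bias is negligible. Neither direction nor size can be settled from the protocol. The dependence of follow-up on birth date can be, and quarter-wide strata bring every scenario with data to the March 2023 cut to 1.00–1.01.

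**What to change.** 1. In the malformation analysis, adjust or stratify by calendar month or quarter of birth or LMP instead of calendar year of delivery.
2. Add an analysis with a common ascertainment age: malformations recorded by 12 months, restricted to births at least 12 months before each database's last infant-diagnosis date. That means births to 31 March 2022 where diagnoses run to the cut, and earlier where they do not, which needs checking for Denmark and Italy. As a sensitivity analysis covering all births, use a shorter common window such as 90 days, where the data reach it. A birth on 31 December 2022 reaches 90 days exactly on 31 March 2023, so there is no allowance for recording lag. Ninety days need not become the main definition, since that would depart from the one-year standard that the protocol cites.
3. Reword section 9.9 to say that under-ascertainment is expected to be related to vaccination through calendar time, and how this is handled.

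The first and third changes cost little. The 12-month analysis loses precision, and how much depends on uptake: it keeps 62% of the birth window (450/725 days), but only 25% of exposed births if these are spread evenly over 2022, and 9% with constant uptake from 21 July 2021. It should therefore support the finely adjusted analysis and not replace it.

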9.10 Other aspects

Not applicable.

10 Protection of human subjects

The proposed studies are non-interventional studies re-using routinely collected health and administrative data. All data collected in the study will be de-identified with no breach of confidentiality with regard to personal identifiers or health information. Each data access provider should apply for an independent ethics committee or other review according to local regulations. Data protection and privacy regulations (GDPR) will be observed in collecting, forwarding, processing, and storing data from study participants. Whenever required by data protection regulations, implicit or explicit cell counts that potentially allow for identification of individuals (e.g., counts of 1-4 in most countries), appropriate masking methods will be applied. All participating investigators/data access providers will obtain all required governance approval for conducting this study. Only aggregate results will be shared. Security processes should be in place to ensure the safety of all systems and data. Every effort should be made to ensure that data are kept secure so that they cannot be accessed by anyone except the study team. Appropriate data storage and archiving procedures will be followed by each DAP and the coordinating center, with periodic backups.

11 Management and reporting of adverse events/adverse reactions

Aggregate analysis of database studies can identify an unexpected increase in risk associated with a particular exposure. Such studies may be reportable as study reports, but typically do not require reporting of individual cases. Moreover, access to automated databases does not confer a special obligation to assess and/or report any individual events contained in the databases. Formal studies conducted using these databases should adhere to these guidelines.

For non-interventional study designs that are based on secondary use of data, such as studies based on medical chart reviews or electronic health care records, systematic reviews or meta-analyses, reporting of adverse events/adverse drug reactions is not required. Reports of adverse events/adverse drug reactions should only be summarized in the study report, where

applicable.^{20 22} According to the EMA Guideline on Good Pharmacovigilance Practices (GVP), Module VI – Management and Reporting of Adverse Reactions to Medicinal Products “All adverse events/reactions collected as part of [non-interventional post-authorization studies with a design based on secondary use of data], the submission of suspected adverse reactions in the form of [individual case safety reports] is not required. All adverse events/reactions collected for the study should be recorded and summarized in the interim safety analysis and in the final study report.” Module VIII – Post-Authorization Safety Studies, echoes this approach. The new legislation further states that for certain study designs such as retrospective cohort studies, particularly those involving electronic health care records, it may not be feasible to make a causality assessment at the individual case level.^{10 23}

[figure not shown]
12 Plans for disseminating and communicating study results

GVP Module VIII: “For studies that are fully or partially conducted by investigators who are not employees of the marketing authorisation holder, the marketing authorisation holder and the investigator should agree in advance on a publication policy allowing the principal investigator to independently prepare publications based on the study results irrespective of data ownership. The marketing authorisation holder should be entitled to view the results and interpretations included in the manuscript and provide comments prior to submission of the manuscript for publication.”²²

The protocol and the final study report will be subject to mandatory publication in the EU PAS register and will comply with ENCePP or Code of Conduct, according to which study results will be published following guidelines, including those for authorship, established by the International Committee of Medical Journal Editors. When reporting results of this study, the appropriate Strengthening the Reporting of Observational Studies in Epidemiology (STROBE),²⁴ RECORD, and RECORD-PE^{25 26} checklist will be followed, and recommendations on reproducible reporting of electronic health care data base studies should be followed.²⁷

Owing to several limitations specific to routinely collected data on pregnancy, only one data extraction is feasible under this protocol. These limitations include: expected low initial number of Spikevax exposed pregnancies; the need to wait for pregnancy end to be identified; different timing of mother-child linkage in different databases; and less frequent (than other databases) data refreshes on birth registries with the largest number of observations and full population coverage (Denmark and Norway). Figure 2 illustrates the data pathway from pregnancy recording to availability for the analysis.

Figure 2. Data pathway from pregnancy recording to availability for the analysis.

To monitor the number of exposed pregnancies, and thus the feasibility of the pregnancy analysis, the number of Spikevax-exposed pregnancies will be approximated from the available pregnancy indicators, such as records of prenatal visits, or diagnostic codes associated with pregnancies. Such records, as a rule, will not be complete with respect to pregnancy outcomes, but are expected to conservatively estimate the number of pregnancies exposed to Spikevax that will be available for the final analysis. Table 6 summarizes the planned contents of the interim and final study reports.

Table 6 Planned data extractions and contents of study reports.

Milestone	Date	Pregnancy data available from each database				
		Denmark	Italy	Norway	Spain	UK
START OF DATA COLLECTION (AT LEAST ONE DAP EXTRACTS DATA in study mRNA-1273-P904)	31-Dec-21					
Study progress report 1 Planned content: status update providing an overview of progress towards finalization of the study design, counts of pregnancies observed in study mRNA-1273-P904 (preliminary pregnancy counts from 31 December 2021 extraction)	31-Mar-22					
Study progress report 2 Planned content: status update providing an overview of project status, counts of pregnancies observed in study mRNA-1273-P904 (preliminary pregnancy counts from 31 December 2021 extraction)	31-Dec-22					

Study progress report 3 Planned content: status update providing an overview of project status, application for data, initial steps towards execution of planned analyses, counts of pregnancies observed in study mRNA-1273-P904 (preliminary pregnancy counts from 31 December 2021 extraction)	30-Jun-23					
END OF DATA COLLECTION (ALL DAPS EXTRACT DATA FOR PREGNANCY ANALYSES)	31-Mar-23					
